## 2.1 Multiplicity Adjustment

Not applicable.

### 3. Analysis Sets

Final decisions regarding the assignment of participants to analysis sets will be made during the review of study data and documented in the final list of important deviations, validity findings and assignment to analysis sets.

For the purposes of analysis, the following analysis sets are defined in Table 3-1. The same definitions apply for Part 1 and Part 2.

Participant analysis set	Assignment rule	
Full analysis set (FAS)	All participants of the respective study part randomized to treatment who fulfilled in/exclusion criteria.	
Per protocol set (PPS)	All FAS participants of the respective study part without validity findings.	
Pharmacokinetic analysis set (PKS)	All participants of the respective study part with PK information not affected by relevant validity findings and with at least one valid post-dose plasma concentration.	
Safety analysis set (SAF)	All participants of the respective study part who took at least one dose of study intervention.	

It is planned to pool the data of participants from Part 1 and Part 2 for analysis, without further stratification by analysis parts, considering that selection criteria and recruitment time periods were identical and all study procedures in Part 2 were performed also in participants enrolled in Part 1. Participants will be analyzed by their actual treatment to which they were treated for most of the time (i.e., placebo or runcaciguat, irrespective of the planned dose they were planned to be titrated to).

The detailed definitions of validity findings and the assignment of participants to the analysis sets will be based on the ACIR document.

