7.1 Discontinuation of study intervention

7.1.1 Permanent discontinuation

In rare instances, it may be necessary for a participant to permanently discontinue (definitive discontinuation) study intervention. If study intervention is permanently discontinued, an End-of-Treatment visit should be performed in line with Visit 15. The participant remains in the study for continued assessment of study outcomes following the visit schedule in section 1.3.

Unscheduled visits may be performed as deemed appropriate by the investigator, in particular in case of withdrawal because of an adverse event.

Participants *must* be withdrawn from the *study intervention* for any of the following reasons:

- Increases in transaminases as described in Table 10-3 (confirmed by analysis of two blood samples; additional laboratory examinations may be performed if necessary):
- Safety concerns for a participant by the investigator or the sponsor, e.g. due to obvious non-compliance.
- Pregnancy (see Section 8.3.5 for details)
- Temporary discontinuation exceeding 14 consecutive days or 21 days overall

Participants *may* be withdrawn from the *study intervention* for any of the following reasons:

- Repeated incidents of relevant hypotension or tachycardia
- Repeated temporary discontinuation of study intervention
- Vision threatening complication or progression to PDR

Necessity to withdraw the participant from the study will be assessed case by case by the investigator.

09 FEB 2023 Page: 45 of 95

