9.3 Analysis sets

For the purposes of analysis, the following analysis sets are defined in Table 9-2.

Participants will be analyzed by their actual treatment (i.e. placebo or runcaciguat, irrespective of the actual dose they were titrated to). It is planned to pool the data of participants from Part 1 and Part 2 for analysis.

Table 9-2 Analysis sets

Participant analysis set	Assignment rule		
Full analysis set (FAS)	All participants of the respective study part randomized to treatment who fulfilled the relevant selection criteria.		
Per protocol set (PPS)	All FAS participants of the respective study part without validity finding.		
Pharmacokinetic analysis set (PKS)	All participants of the respective study part without validity findings affecting the PK analysis and with ≥ 1 valid PK samples who received at least one dose of study intervention.		
Safety analysis set (SAF)	All participants of the respective study part who took \geq 1 dose of study intervention.		

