#### 4.1.4 Discontinuations

Participants who discontinue the study prematurely (i.e., dropout) will not be replaced. A temporary discontinuation exceeding 14 consecutive days or 21 days overall results in a permanent discontinuation. If unexpectedly high dropout rates occur (e.g., due to COVID-19), the number of randomized participants may be increased by up to 20%. For further details with respect to the analysis of dropouts refer to the Section 4.1.3 on handling of Missing Data.

A participant may withdraw from the study at any time at his/her own request or may be withdrawn at any time at the discretion of the investigator for safety, behavioral, or compliance reasons. This includes cases where, in the investigator's opinion, continued participation in the study would be harmful to the participant's well-being. This is expected to be uncommon. At the time of discontinuing from the study, if possible (if the participant is not lost to follow-up and if the health status of the participant allows), Visit 15 should be conducted as early discontinuation visit, followed by safety follow-up (Visit 16). Data collected at early discontinuation visits will be handled as follows: If a valid DRSS assessment is available from the early discontinuation visit, this value will be considered for analyses for the respective visit. Other variables assessed at early discontinuation visits will be listed for individual follow-up but not be considered for summary statistics.

Participants who permanently discontinue study treatment are invited to continue to attend all protocol-specified study visits. Values assessed at visits after discontinuation from study treatment will be listed for individual follow-up but not be considered for summary statistics. All values assessed after study treatment discontinuation will be flagged in the listings.

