## 4.2.2 Main Analytical Approach

For the primary analysis, the last observation before missing DRSS values will be carried forward (LOCF) to impute missing values if the participant dropped out after visit 9 (week 12) and the EoT DRSS assessment was performed within 4 weeks of treatment discontinuation (*while on treatment strategy*). If the last measured DRSS score already showed an improvement by  $\geq 2$  steps at the last measurement prior to the missing assessment, the participant will be considered a responder for the primary endpoint. Otherwise, the participant will be considered a non-responder. If the participant dropped out after visit 9 (week 12) and the EoT DRSS assessment was performed more than 4 weeks after treatment discontinuation the last available DRSS assessment prior to treatment discontinuation will be used (LOCF) (*while on treatment strategy*). Participants who dropped out before visit 9 (week 12), or who had a VTC in the study eye prior to the missing assessment will be considered non-responders regardless of the DRSS level (*composite variable strategy*).

Treatment groups will be runcaciguat and placebo, actually administered dose levels will not be considered for this analysis.

Primary efficacy analyses will be performed on the PPS and will include only study intervention compliant participants (*principal stratum strategy*). In addition, sensitivity analyses will be performed on the FAS. Further analyses may include a separate analysis for each runcaciguat maintenance dose level that was reached during titration (on the PPS). Participants will be analyzed according to the treatment (i.e., runcaciguat or placebo) they actually received.

The study will be analyzed using Bayesian inference with non-informative priors. PoC shall be defined as fulfillment of the following criteria:

•  $P(\pi_{ACT} - \pi_{PLC} > 0 | data) \ge 0.9$ i.e., the posterior probability that the difference between  $\pi_{ACT}$  and  $\pi_{PLC}$  is greater than 0 (clinical activity) given the data observed in the study needs to be 90% or more,

and

•  $P(\pi_{ACT} > 0.25 | data) \ge 0.5$ i.e., the posterior probability that  $\pi_{ACT}$  is greater than 0.25 (clinical relevance) given the data observed in the study needs to be 50% or more.

95% credible intervals will also be presented for  $\pi_{ACT}$  and for  $\pi_{PLC}$ 

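### The FAS check on the per-protocol proof-of-concept result is not made on the groups as randomised, and the SAP is inconsistent on whether an off-treatment Week-48 DRSS counts

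*SAP*

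**What the plan says.** **Who is in the FAS.** SAP section 3 (Table 3-1) defines it as "All participants of the respective study part randomized to treatment who fulfilled in/exclusion criteria". Protocol section 9.3 has the same restriction: "All participants of the respective study part randomized to treatment who fulfilled the relevant selection criteria". SAP section 3 leaves final assignment to the review of study data and refers to the ACIR document for the detailed definitions of validity findings.

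**How participants are grouped.** SAP section 3 states for all analysis sets: "Participants will be analyzed by their actual treatment to which they were treated for most of the time". SAP 4.2.2, which covers both the per-protocol primary analysis and its FAS repeat, says: "Participants will be analyzed according to the treatment (i.e., runcaciguat or placebo) they actually received". Protocol 9.3 also groups by actual treatment.

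**Which outcomes count.** SAP 1.1 makes the FAS estimand the same as the primary one, less the compliance condition. The FAS therefore keeps the while-on-treatment rule, under which a DRSS taken more than 4 weeks after stopping gives way to the last on-treatment value. Protocol 7.1.1 keeps people who stop treatment under observation: "The participant remains in the study for continued assessment of study outcomes following the visit schedule in section 1.3". SAP 4.1.4 says of their later visits: "Values assessed at visits after discontinuation from study treatment will be listed for individual follow-up but not be considered for summary statistics".

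**Other checks.** The multiple-imputation analysis (SAP 4.2.3) and the subgroup analyses (SAP 4.2.4) are on the per-protocol set.

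**The concern.** A per-protocol primary analysis removes people for what happened after randomisation. The usual safeguard is a companion analysis on everyone randomised, in the arm to which they were assigned. Here the companion restores the non-compliant participants but still drops some randomised people and groups the rest by treatment received. The FAS has no dose requirement, so a randomised participant who never took a tablet belongs to it yet has no arm under the grouping rule.

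Separately, SAP version 2.0 introduced the estimands in order to use all available data, including data from early discontinuers. Yet the Week-48 photograph of someone who stopped treatment and stayed in the study may go unused.

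The decision has an absolute criterion on the active arm alone (response above 25%), so it depends on who remains in that arm's denominator. Protocol 2.1 makes the trial the basis for a general decision on sGC activators in NPDR.

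**Working it through.** **1. The plan's own figure.** Inputs from Protocol 9.2 and SAP section 5: 40 evaluable per arm, true rates 35% and 10%, and a Beta(0.5, 0.5) prior in each arm. With k responders of n the posterior is Beta(k + 0.5, n − k + 0.5). PoC requires P(π_ACT > π_PLC | data) ≥ 0.90 and P(π_ACT > 0.25 | data) ≥ 0.50. Exact enumeration over the two binomials gives P(PoC) = 90.3%, which agrees with the stated 90% or more. That figure is not in dispute.

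**2. Sensitivity to the denominator.** The relevance probability is 1 − F(0.25; k + 0.5, n − k + 0.5), where F is the Beta distribution function.

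| Active arm | Placebo | Relevance | Activity | PoC |
|---|---|---|---|---|
| 10/40 | 5/40 | 0.512 | 0.925 | met |
| 10/41 | 5/40 | 0.476 | 0.917 | not met |

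One extra active non-responder reverses the decision. With all 52 active participants counted, 13 responders are needed (12/52 gives 0.384, 13/52 gives 0.511).

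**3. Is an observed off-treatment Week-48 DRSS used?**

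| Place | Points to |
|---|---|
| SAP 1.1, intercurrent events | Not used if taken more than 4 weeks after stopping |
| SAP 4.1.4, visits after treatment discontinuation | Not used (listed only) |
| SAP 4.1.4, early discontinuation visit | A valid DRSS from that visit is used |
| SAP 4.2.2 | Carries forward for missing values in those who dropped out; for dropouts assessed more than 4 weeks after stopping, uses the last on-treatment value |
| SAP 4.2.3 | Imputes only when the Visit 15 DRSS is missing |
| Protocol 9.4.2 | Imputes only missing data |

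SAP 4.1.4 equates dropping out with leaving the study. On that meaning, someone who stops tablets but attends Visit 15 is not a dropout and has nothing missing. The while-on-treatment label and the listing rule point the other way. If the value is set aside, that departs from Protocol 9.4.2, and SAP 4.8 does not list it.

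**4. Possible size of the carry-forward effect (assumed inputs).** Suppose 18% stop treatment (borrowed from the non-evaluable share, 18/98 = 18.4%) and a fraction L of their carried-forward responses is lost by Week 48. The rate is then 0.35 × 0.82 + 0.35 × 0.18 × (1 − L):
- L = 0.25: 0.287 + 0.047 = 33.4%
- L = 0.50: 0.287 + 0.032 = 31.9%

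**5. What an all-randomised run would show (52 versus 46; off-treatment shares assumed).**

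| Off-treatment share | P(PoC) if that share of the active arm responds at 10% | P(PoC) if that share of both arms are non-responders |
|---|---|---|
| 0% | 93.5% | 93.5% |
| 5% | 91.0% | 90.4% |
| 10% | 87.8% | 85.9% |
| 18% | 81.0% | 75.3% |

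**The case against.** Several points on the other side stand.

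- **Both departures should be rare.** Assignment is central and masked with numbered bottles, and no crossover is planned, so as-treated differs from as-randomised only after a sustained dosing error. Eligibility rests on screening or pre-dose criteria, the reading centre confirms baseline DRSS, and waivers are barred. The sponsor study team (apart from the bioanalytical/PK group) and the outcome assessor are masked. Nothing suggests exclusions that depend on arm or outcome. What remains is that the SAP does not require ineligibility to be judged on pre-randomisation information alone.
- **A reader might infer that the SAP plainly discards the observed off-treatment Week-48 DRSS.** It does not say so; the sections conflict, as set out above. A DRSS within 4 weeks of stopping is used, and vision-threatening complications are followed after treatment ends.
- **A reader might infer that setting off-treatment data aside breaks randomisation.** It is an estimand choice and leaves the groups intact. Only the eligibility exclusion and the as-treated grouping change them.
- **A reader might infer that exclusions materially inflate the chance of success.** If five active non-responders are removed, the cut-off falls from 13/52 to 12/47, and the chance of meeting the relevance criterion rises from 0.553 to 0.677 at a true 25% and from 0.228 to 0.341 at 20%. That mimics per-protocol compliance exclusions, which the FAS already reverses, and assumes that all five are non-responders. Removal unrelated to outcome gives 0.522 and 0.217, slightly lower than with nobody removed.
- **The carry-forward illustration is mild.** It stays well above 25%, and 18% is not a treatment-stopping rate. Dropouts before Week 12 and complications preceding a missing assessment already count as non-response, so fewer responses are carried forward.

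**Conclusion.** The point holds as a gap in the sensitivity analyses. Neither document plans a run of the PoC rule on all randomised participants, grouped as randomised, with observed Week-48 outcomes. The FAS reverses the compliance exclusions but keeps the eligibility restriction, the as-treated grouping and the while-on-treatment rule. On an observed Week-48 DRSS more than 4 weeks after stopping, the finding is inconsistency between sections, not proven exclusion.

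The size cannot be derived from the documents, which give no rate for dosing errors, eligibility violations or treatment stopping. It is probably small. The reason to act is that the relevance criterion can turn on one participant (10/40 against 10/41) and the data for the check are already to be collected. The primary result is not invalidated, and the 90% design figure stands.

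**What to change.** Keep the primary estimand, and make these changes before unmasking:

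1. Add one supplementary run of the PoC rule on all randomised participants, grouped as randomised, with no dose requirement. Use the observed Week-48 DRSS regardless of treatment discontinuation. Count a vision-threatening complication in the study eye, or a missing Week-48 DRSS, as non-response.
2. Group the FAS efficacy analyses as randomised, and keep as-treated grouping for safety.
3. State in SAP 4.2.2 how the primary analysis handles a Week-48 DRSS observed after treatment discontinuation in someone who stayed in the study, and align SAP 1.1 and 4.1.4 with it.
4. Record the changes in SAP 4.8, because the FAS definition and the as-treated rule also stand in Protocol 9.3.

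A supplementary run is preferable to redefining the FAS in the SAP alone, which would put the SAP at odds with the protocol. Requiring at least one dose would add a post-randomisation condition that the FAS does not now have.

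The cost is SAP text and one table from data already collected. The drawback is that the table may show a diluted estimate beside the primary one, so it should be labelled supplementary and not as a second decision rule.

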#### 4. Statistical Analyses

#### 4.1 General Considerations

#### 4.1.1 General Principles

The SAP will be finalized prior to unmasking.

The statistical evaluation will be performed by using the software SAS (release 9.4 or higher; SAS Institute Inc., Cary, NC, USA) and R (version 3.5.2 or higher; R Foundation for Statistical Computing, Vienna, Austria).

All data will be listed and summarized in tables. Graphical illustrations will be provided by treatment group (runcaciguat, placebo) where appropriate. Summary statistics will be presented for the participants treated with runcaciguat and for the participants treated with placebo. Descriptive statistics by visit will be provided for the original data as well as for change from baseline, where applicable. Additional summary statistics per dose of runcaciguat administered will be presented, where meaningful. Doses may be grouped to reach more meaningful sample sizes. Frequency tables will be provided for qualitative data.

Continuous variables assumed to be normally distributed will be summarized using the number of participants, mean, standard deviation, minimum, lower quartile, median, upper quartile and maximum. The geometric mean and SD will be provided additionally for the variables where log-normal distributions are assumed.

Generally, data will be analyzed comparing the two intervention groups against each other.

Furthermore, for the runcaciguat treatment group, summary statistics by visit for continuous variables will be further broken down by the actual maintenance dose level, i.e., the dose level reached after the end of the titration phase (at Visit 6) (in case a sufficient number of patients pertains to this dose level).

Data from unscheduled measurements will be listed, but not included in summary statistics or frequency tables.

Listings will be provided sorted by treatment group (runcaciguat, placebo), DRSS at baseline (47, 53) and participant identifier.

Baseline is defined as the last pre-dose assessment before first study intervention.

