In case of clinically relevant abnormal laboratory results, the investigator has the discretion to perform unscheduled repeat laboratory examinations earlier than at the intervals provided in the SoA in Section 1.3. These unscheduled examinations should be processed by the central lab to ascertain that the data will be included in the database. At the investigator's discretion, additional laboratory parameters may be investigated and samples may be processed by the local lab. In case of relevant liver enzyme elevation (see also Section 10.5), the investigator should perform a repeat serum chemistry panel 2 times per week (including serum transaminases [AST and ALT] and serum bilirubin), frequency of retesting can decrease to once a week if laboratory abnormalities decrease and participant is asymptomatic.

Estimation of glomerular filtration rate (eGFR)

eGFR will be calculated using CKD-EPI formula, using the serum creatinine concentration measured at screening (Kidney Disease: Improving Global Outcomes (KDIGO) CKD Work Group 2013). The calculation will be done by the central laboratory. In case of a decrease by \geq 40%, a critical alert will be provided to the investigator, as it may represent a reason for treatment discontinuation, as described in Section 7.1.2.

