#### 4.5.2 Adverse Events

Individual listings of all AEs will be provided indicating whether the AE is treatmentemergent or treatment-emergent related to study intervention and including AE onset relative to start of treatment, the actual dose (or sham titration) level at the start of the AE, and the duration of the AE.

AEs will be summarized using the MedDRA terms by SOC, HLGT (if feasible) and PT.

The following AEs have been defined as AESIs and are recorded as such:

- AEs suggestive of hepatic injury,
- Syncope/loss of consciousness,
- Acute kidney injury suggested by 2.0-fold increase in serum creatinine or >50% decrease in eGFR.

The number of participants with at least one such event in the following TEAE categories will be given by treatment and total:

- Any AE
- any TEAE,
- any mild, moderate, severe TEAE (maximum intensity),
- any TEAE related to study intervention,
- any mild, moderate, severe TEAE related to study intervention,
- any TEAE related to study procedures,
- any treatment emergent SAE,
- any TEAE leading to death,
- any treatment emergent SAE related to study intervention,
- any TEAE leading to not up-titrating study intervention,
- any TEAE leading to dose reduction of study intervention,
- any TEAE leading to interruption of study intervention,

- any TEAE leading to permanent discontinuation of study intervention, and
- any treatment emergent AESI (also broken down by category of special interest as stated above).

These frequency tables will also be presented broken down by maximum intensity of the TEAEs, where appropriate.

Individual listings will be provided for serious TEAE, deaths, treatment emergent AESI, TEAE leading to study intervention interruption, TEAE leading to not up-titrating study intervention, TEAEs leading to study intervention reduction, and TEAEs leading to study intervention discontinuation.

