#### 4.5.3 Laboratory assessments

- HbA1c
- Triglycerides
- HDL- / LDL-/ total serum cholesterol
- Further parameters are detailed in Section 10.2 of the CSP

Continuous laboratory values will be summarized descriptively by parameter including absolute changes from baseline. Frequency tables will be provided for qualitative data.

In addition, the frequencies for liver abnormality criteria as defined in CSP Section 10.5 will be presented:

- ALT or AST  $>3 \times ULN$ ,
- ALT or AST >3 x ULN and Total bilirubin >2 x ULN,

- ALT or AST >3 x ULN and INR >1.5 x ULN,
- ALT or AST >5 x ULN for more than 2 weeks,
- ALT or AST >8 x ULN.

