#### Table 4-1: Formula for eGFR calculation

 $GFR = glomerular filtration rate in mL/min/1.73 m^2$ , eGFR = Estimated glomerular filtration rate, SCr = Serum creatinine

The eGFR values based on serum creatinine are assumed to be log-normally distributed and will be summarized descriptively including relative changes from baseline with 95% CI. The eGFR values will be summarized using summary statistics as defined for log-normally distributed variables.

Geometric mean eGFR including one SD range over time will be plotted. Individual plots of eGFR values will also be presented by stratum (DRSS at baseline) and treatment group.

A frequency table will be presented summarizing decreases in eGFR values from baseline by >50%, >40%, >30%, etc. including cumulative frequencies. Decrease in eGFR [%] will be calculated as 1- (eGFR post-dose / eGFR at baseline) \*100.

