## 4.5.6 Additional Safety Assessments

## ECG

During Part 1 up to study Visit 6 (inclusive), triplicate ECG tracings will be recorded. These triplicate tracings may be transferred to a central ECG reading center for later QT evaluation. The results of the QT evaluations may be reported separately. For part 2, single ECGs will be recorded and transferred to a central ECG reading center for evaluation.

ECG parameters (ventricular rate, PR interval, QRS-duration, and QT interval) will be determined and transferred to the database. The QT interval will also be corrected for the heart rate using Fridericia's method (QTcF), i.e., by dividing the observed QT interval by the cube-root of RR:

$$QTcF = \frac{QT}{\sqrt[3]{RR}}$$

Corrected QT intervals and the heart rate will be provided by the central ECG lab and summarized descriptively by parameter including absolute changes from baseline.

A frequency table will be provided for the ECG findings, presence of sinus rhythm and atrial fibrillation and overall interpretation of ECGs (normal; abnormal, clinically insignificant; abnormal, clinically significant), by visit including any visit.

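### Applied as written, the SAP's exclusion of unscheduled values lowers the liver threshold counts, most of all the two-week ALT/AST row; the eGFR effect is small

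*SAP*

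**What the plan says.** The general rule is in SAP 4.1.1: "Data from unscheduled measurements will be listed, but not included in summary statistics or frequency tables". Two later sections ask for counts of participants crossing a laboratory threshold:

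- SAP 4.5.3: "In addition, the frequencies for liver abnormality criteria as defined in CSP Section 10.5 will be presented". Five criteria follow, one of which is "ALT or AST >5 x ULN for more than 2 weeks".
- SAP 4.5.4: "A frequency table will be presented summarizing decreases in eGFR values from baseline by >50%, >40%, >30%, etc", with cumulative frequencies.

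Neither section mentions unscheduled samples or a worst-value rule. The ECG table in SAP 4.5.6 is the only one of these outputs to ask for a count across visits: "by visit including any visit".

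The protocol produces the excluded samples. For a relevant liver enzyme elevation, Protocol 8.2.4 states that "the investigator should perform a repeat serum chemistry panel 2 times per week". Protocol 10.5 puts the frequency at up to twice weekly, and allows it to drop to weekly or less once values fall and the participant has no symptoms. Protocol 7.1.2 asks for confirmatory tests after an eGFR fall of 40% or more. Of off-schedule repeats, Protocol 8.2.4 says: "These unscheduled examinations should be processed by the central lab to ascertain that the data will be included in the database".

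SAP 4.1.4 adds a second restriction. Early-discontinuation-visit values other than DRSS, and values after treatment has stopped, are listed but left out of summary statistics.

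**The concern.** The criteria that SAP 4.5.3 counts are the ones that trigger off-schedule sampling. If the repeats are then barred from the table, a criterion first met on a repeat appears in a listing and in no count. A duration criterion is worse placed, because it needs at least two values and the repeats are how the protocol obtains the second.

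Safety is the secondary objective, and Table 2-2 of the protocol names liver enzyme elevation and renal impairment as potential risks. For a given set of samples the rule can only lower a count. With 52 participants planned on runcaciguat and 46 on placebo, one uncounted participant is 1/52 = 1.9 or 1/46 = 2.2 percentage points.

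**Working it through.** The plan gives no figure for this point, so there is none to reproduce. The check sets the texts side by side, takes a bound from the visit schedule, and adds an illustration.

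**1. Is the rule lifted anywhere?** SAP 4.5.4 calls its output a frequency table, which is the term used in SAP 4.1.1. SAP 4.5.3 says frequencies. Neither states an exception. SAP 4.1.3 says that all valid observed data are considered, but that sentence is general and the one on unscheduled data is specific.

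**2. Scheduled chemistry after baseline** (Protocol Tables 1-2 to 1-4): days 8, 15, 22, 29, 43, 57, 85, 113, 141, 169, 225, 281, 337 and 365. The gaps are 7 days to day 29, 14 to day 57, 28 to day 169, 56 to day 337, then 28.

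**3. Bound for the two-week row.** Scheduled values alone fill the row only if two of them, more than 14 days apart, lie in the same elevation. From day 169 to day 337 the visit windows are ±7 days, so the smallest gap is 56 − 7 − 7 = 42 days. An elevation of 15 to 41 days inside that period is long enough to qualify but cannot contain two scheduled samples.

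**4. Illustration.** Assumptions, none of them from the documents:
- the elevation above 5 x ULN is constant;
- onset is uniform, with the whole episode inside days 1 to 337;
- each visit is uniform within its Part 2 window;
- repeats start after the first scheduled crossing;
- the row is met when the first and last values above 5 x ULN are more than 14 days apart.

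The simulation used 400,000 episodes per duration. Protocol 8.2.4 and 10.5 differ on repeat frequency, so both cases are shown.

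| Episode length | Scheduled only | Repeats every 3.5 days | Difference | Weekly repeats | Difference |
|---|---|---|---|---|---|
| 21 days | 4.1% | 15.5% | 11.4 | 5.9% | 1.8 |
| 28 days | 11.5% | 37.0% | 25.5 | 28.7% | 17.2 |
| 42 days | 30.5% | 68.0% | 37.5 | 62.1% | 31.6 |
| 56 days | 49.5% | 87.0% | 37.5 | 84.2% | 34.7 |

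The differences, in percentage points, are what the exclusion removes. What is still missed with repeats is due to the visit schedule. The 21-day weekly difference is best read as close to nil. On a strict weekly series the first repeat more than 14 days after the first crossing comes at 3 × 7 = 21 days, when the episode is over.

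**5. Hand check for days 169 to 337 at nominal visit days.** With repeats every 3.5 days, the first one more than 14 days after the crossing comes at 5 × 3.5 = 17.5 days. An episode of L days therefore qualifies if a scheduled sample falls in its first L − 17.5 days. Only days 225 and 281 can supply that sample, and onset is spread over 168 − L days:

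proportion = 2(L − 17.5) / (168 − L)

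- L = 21: 7/147 = 4.8% (simulated with windows: 5.7%)
- L = 28: 21/140 = 15.0% (16.3%)
- L = 42: 49/126 = 38.9% (40.2%)
- L = 56: 77/112 = 68.8% (68.9%)

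Scheduled values alone give 0.0%, 0.0%, 0.0% and 4.2% in the simulation. The hand calculation and the simulation agree closely.

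**6. eGFR.** The repeat in Protocol 7.1.2 follows a fall already at 40% or more. If a scheduled visit triggered it, the participant is already in the >30% band and, unless the fall is exactly 40%, in the >40% band. The repeat can newly reach only >50%. The kidney AESI (Protocol 8.3.6) is defined by the same >50% fall or by a doubling of creatinine. The two lower bands are missed only when the crossing is first seen on some other unscheduled sample.

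**7. SAP 4.1.4.** Four of the five liver rows in SAP 4.5.3, all except the plain 3 x ULN row, carry treatment withdrawal in Protocol Table 10-3. Many follow-up values for these participants will therefore come from after treatment. SAP 4.1.4 names summary statistics only, so its reach to criterion counts is unclear and needs to be settled in the same edit.

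**The case against.** The best counter-argument comes from INR. It is not in the required panel (Protocol Table 10-1) and appears only in the liver work-up list (Table 10-4), so every INR value is off schedule. If SAP 4.1.1 governed the liver rows, the planned INR row could never be filled, which suggests that the authors did not mean it to apply. SAP 4.5.3 also imports its criteria from Protocol 10.5, where repeat sampling is part of the procedure, and the TLF specifications are a separate document that may settle the matter. This shows that the SAP conflicts with itself. It does not supply the missing exception, and a programmer following SAP 4.1.1 would produce the lower counts.

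The second argument is that little is lost. Unscheduled values are listed, and Protocol 9.4.5 promises tables of abnormal values. SAP 4.5.2 counts "any treatment emergent AESI (also broken down by category of special interest as stated above" and TEAEs leading to discontinuation, whatever the visit type. These are descriptive tables in a proof-of-concept study, and no PoC criterion uses them. All of this stands and limits the severity. Still, listings and abnormal-value tables do not count participants per criterion by arm, and AESI counts depend on what the investigator reports.

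A reader might infer that the >30% and >40% eGFR bands are seriously undercounted because they have no AESI counterpart. The documents do not support that: a confirmatory sample prompted at a scheduled visit cannot newly place anyone in those bands (step 6). Nor do the acute kidney injury rates from the CKD study (2.7% and 1.7%) measure the loss. They are adverse events in another population, of a kind that the unaffected tables would count.

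**Conclusion.** The point holds for the liver criteria, chiefly the two-week row, and only weakly for eGFR. The text-based part rests on SAP 4.1.1 being applied as written, and the 42-day bound follows from the visit schedule alone. The losses of about 11, 26, 38 and 38 points (twice-weekly repeats) or 2, 17, 32 and 35 points (weekly) illustrate one row under assumed episode lengths and onset. They are not estimates for this trial. The actual undercount cannot be computed from the documents; its direction is downward. First crossings at scheduled visits are counted.

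It would go too far to say that the safety signal is lost: the values remain in listings, and the AE, AESI and discontinuation tables are untouched. Severity is minor to moderate.

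**What to change.** - **SAP 4.1.1:** limit the exclusion to by-visit summary statistics and by-visit frequency tables.
- **SAP 4.5.3 and 4.5.4:** state that, notwithstanding 4.1.1 and 4.1.4, each participant is counted once per criterion from all post-baseline values in the database (scheduled, unscheduled and discontinuation-visit), from first dose to 28 days after last dose. Use the worst value for single-value criteria and the sequence of values for the two-week criterion.
- **INR row:** give as denominator the number of participants with INR measured.
- **Context:** show the number of participants with unscheduled samples by arm, because arms may differ in how often repeats are taken and more sampling finds more crossings.

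The cost is a few SAP sentences and minor programming before unmasking. No new data are needed where repeats went through the central laboratory. Extra parameters run locally may not be in the database, and the table should say so.
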